### **16.3 Other Endpoint Analyses**

#### **Relapse Assessment:**

The qualitative variables

- Subject experienced any MS relapses since last visit (Yes / No)

will be summarized for month 6, month 12 using descriptive statistics from Safety Analysis Set.

The quantitative variable

- No. of Relapses since last visit

will be summarized for month 6, month 12 as number and percentage from Safety Analysis Set.

Listing will be provided for Relapse assessment.

### **17. Safety Evaluation**

Safety evaluation includes the summary of safety endpoints such as adverse events, vital signs, physical examination and neurological examination during the study based on Safety Analysis Set.

#### **17.1 Adverse Events**

Adverse events will be summarized per subject using number and percentage by SOC and PT from Safety Analysis Set. If an adverse event is reported for a subject more than once during

treatment, the worst severity and the worst relationship to trial treatment will be tabulated. Listings will also be provided for all the adverse events.

Adverse events will be coded using MedDRA version 19.1.

### **17.1.1 All Adverse Events**

All Adverse events will be summarized using number and percentage by MedDRA-SOC and PT within SOC for relationship, severity and Action taken with Study Medication. The adverse events reported under the category 'Related' will be considered as treatment-related adverse events. Missing will also be considered as related to the treatment. PT within SOC and primary SOC will be given in alphabetical order from Safety Analysis Set.

### **17.1.2 Adverse Events Leading to Trial and Treatment Discontinuation**

AEs leading to treatment discontinuation and study termination will be summarized using number and percentage by MedDRA-SOC and PT within SOC from Safety Analysis Set.

If the primary reason for discontinuation is "Discontinuation of Rebif is desired or considered necessary by the Investigator and/or the subject" and "Discontinuation of Rebif for any other reason" will be considered for the treatment discontinuation reasons.

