## 7. Sample Size

A sample size of 106 subjects will be required to have 85% power to detect at least an 8 point difference in mean TSQM scores between Baseline and Month 6 or Month 12 measurements, with the standard deviation (SD) of 27.5 and a two sided significance level of 5%. Assuming a 20% drop out rate, approximately 133 patients will be enrolled into the study in the Netherlands, Switzerland and Belgium.

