## **12. Trial Subjects**

### **12.1 Disposition of Subjects and Discontinuations**

A table with

- Number of subjects screened
- Number of screen failure subjects
- Number of subjects enrolled in the study
- Number of subjects in Safety Analysis Set
- Number of Safety Analysis Set subjects who completed the study.
- Number of Safety Analysis Set subjects who discontinued the study together with primary reason for discontinuation (Lost to follow-up, Adverse event/ Serious adverse event, Discontinuation of Rebif is desired or considered necessary by the Investigator and/or the subject, Occurrence of an exclusion criterion, Subject withdraws consent (Reasons for Withdraws consent), Discontinuation of Rebif for any other reason (Reason for discontinuation)).

will be presented. Percentages will be calculated.

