### **17.2.2 Serious Adverse Events**

Serious adverse events (SAEs) will be summarized per subject using number and percentage by SOC and PT from Safety Analysis Set.

All SAEs will be summarized using number and percentage by MedDRA-SOC and PT within SOC for relationship and Action taken with Study Medication. The SAEs reported under the

category 'Related' will be considered as treatment-related SAEs. Missing will also be considered as related to the treatment. PT within SOC and primary SOC will be given in alphabetical order from Safety Analysis Set.

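### Section 17.1.2 identifies treatment discontinuation from two subject-level reasons that do not name an adverse event, and does not say where the adverse-event reason belongs

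*SAP*

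**What the plan says.** Section 17.1.2 of the SAP states that "AEs leading to treatment discontinuation and study termination will be summarized using number and percentage" by system organ class and preferred term. A second sentence then names two primary reasons, "Discontinuation of Rebif is desired or considered necessary by the Investigator and/or the subject" and discontinuation of Rebif for any other reason, which "will be considered for the treatment discontinuation reasons". That is the only rule given for building the table.

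The reasons come from the disposition table in section 12.1, which records one primary reason for each subject who left the study. AE/SAE is a category of its own there, next to the first of the two Rebif reasons: "Adverse event/ Serious adverse event, Discontinuation of Rebif is desired or considered necessary by the Investigator".

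The SAP also plans an AE-level variable on what was done with the drug. Section 17.1.1 tabulates all AEs for "relationship, severity and Action taken with Study Medication", and section 17.2.2 tabulates serious AEs "for relationship and Action taken with Study Medication". Section 17.1.2 refers to neither.

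**The concern.** A table of AEs that ended treatment should be driven by AEs. Here the rule works on a subject-level reason, uses two reasons that can apply without any AE, and is silent on the one reason that names an AE. The sentence is also grammatically incomplete, and it joins the two reasons with *and* although a subject has a single primary reason. A programmer would have to guess what is meant.

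At stake is a figure that readers will look for. The rationale in section 6 describes other first-line drugs by their discontinuation rates due to adverse events, so the natural question is what the matching figure is for Rebif. The table in 17.1.2 is where they would look, and its content depends on the guess.

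**Working it through.** There is no stated figure to reproduce. The check compares two lists and then asks what the rule selects.

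**Step 1. Compare the lists.**

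| Primary reason (12.1) | Names an AE? | Placed by 17.1.2 |
|---|---|---|
| 1. Lost to follow-up | No | Not placed |
| 2. AE/SAE | Yes | Not placed |
| 3. Rebif stop wanted or judged necessary | No | Treatment discontinuation |
| 4. Exclusion criterion occurs | No | Not placed |
| 5. Consent withdrawn | No | Not placed |
| 6. Rebif stop for any other reason | No | Treatment discontinuation |

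Two of the six reasons are mapped, and neither names an AE. With one primary reason per subject, someone coded under reason 2 cannot also be under 3 or 6.

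**Step 2. What the rule selects.** For reason k, let a_k be the subjects with an AE that ended Rebif, and b_k the subjects who have AEs, none of which ended Rebif. Restrict attention to reasons 2, 3 and 6.

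- Wanted: a2 + a3 + a6.
- Rule as written, with no filter at AE level: a3 + a6 + b3 + b6. Error = b3 + b6 − a2.
- Same rule with an unstated filter for AEs that caused the stop: a3 + a6. Error = −a2.
- AE/SAE taken as included although not named, with that filter: a2 + a3 + a6. Error = 0.
- AE/SAE taken as included, no filter: error = b2 + b3 + b6.

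The SAP states neither the filter nor the inclusion. The error may therefore be negative, zero or positive.

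**Step 3. Can it be sized?** Section 7 gives only a planning figure: "Assuming a 20% drop out rate, approximately 133 patients will be enrolled into the study". That is 133 × 0.20 = 26.6, or 133 − 106 = 27 leavers. The split by reason is not given. Letting the AE/SAE share run from 0% to 100% gives 0 to 27 subjects for reason 2, which says nothing useful, and b3 and b6 have no planning value at all. No estimate can be made.

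**The case against.** The best defence is that 17.1.2 nowhere limits treatment discontinuation to the two named reasons. Its heading already concerns AEs leading to discontinuation, so AE/SAE may be covered by the heading, with the second sentence only adding two labels that do not mention an AE. The plan may also intend one combined summary, since nothing fixes two tables or two columns. An AE that ended both Rebif and participation would then appear once, in the right place. Further, the study is non-interventional, so leaving it need not mean stopping Rebif; mapping exactly the two reasons that mention stopping Rebif is literal and coherent; and a stop judged necessary by the investigator may itself be due to an AE.

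Part of this stands. A reader might infer that AEs of subjects coded AE/SAE are definitely omitted and that AE-driven Rebif discontinuation is understated. The document does not support that. It does not exclude AE/SAE, it does not establish a separate treatment-discontinuation part, and a one-way shortfall requires an AE-level filter that it does not state.

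The defence does not remove the fault. Neither the additive nor the combined reading is written in the SAP. Even if both were adopted, AEs would still be selected through reasons that do not concern AEs, and AEs of subjects who stopped Rebif for other causes could still enter.

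It is also true that the information is not lost. Section 12.1 counts AE/SAE leavers, 17.1.1 and 17.2.2 show action taken, and section 17.1 promises that "Listings will also be provided for all the adverse events". This limits the consequence; it does not make the table right.

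**Conclusion.** The rule in 17.1.2 is badly fixed. It keys a table of AEs to two subject-level reasons that do not name an AE and leaves the AE/SAE reason without a place. Applied as written, it can miss AEs that ended Rebif and can admit AEs that did not.

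Severity is minor. One descriptive safety table is affected, and the primary endpoint is not. The direction and number of misclassified subjects cannot be derived from the SAP. The conclusion rests on the text of 12.1 and 17.1.2, and on one primary reason being recorded per subject. How sites code an AE-driven stop depends on the CRF, which is not shown.

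**What to change.** Replace the mapping sentence in 17.1.2 with wording such as:

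*AEs leading to treatment discontinuation are AE records whose Action taken with Study Medication is permanent discontinuation of Rebif (category as on the CRF), whatever the primary reason in section 12.1. AEs leading to study termination are those of subjects whose primary reason is Adverse event/ Serious adverse event, with the responsible AE identified at data review before database lock. A subject may count in both.*

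This corrects both possible errors, because selection moves to the AE record. It is a reporting definition only and sets no rule for when treatment stops.

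The cost is a few sentences of SAP text and one changed table filter. The action-taken variable is already planned for 17.1.1 and 17.2.2, and section 12.2 already foresees identifying outliers before database lock. The category label for permanent discontinuation must be checked against CRF version 3.0, cited in section 19. If the CRF also links an AE to study termination, that link can replace the data-review step.

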## **17.2 Deaths, Other Serious Adverse Events, and Other Significant Adverse Events**

### **17.2.1 Deaths**

If any death is reported it will be presented as case narrative. Listing will be provided for death cases.

### **17.2.2 Serious Adverse Events**

Serious adverse events (SAEs) will be summarized per subject using number and percentage by SOC and PT from Safety Analysis Set.

All SAEs will be summarized using number and percentage by MedDRA-SOC and PT within SOC for relationship and Action taken with Study Medication. The SAEs reported under the

category 'Related' will be considered as treatment-related SAEs. Missing will also be considered as related to the treatment. PT within SOC and primary SOC will be given in alphabetical order from Safety Analysis Set.

### **17.3 Clinical Laboratory Evaluation**

Not applicable

### **17.4 Vital Signs**

Vital sign parameters such as Systolic blood pressure (mmHg), Diastolic blood pressure (mmHg), Weight (Kg) and Height (Cm) will be assessed at all available visits. These parameters will be summarized using descriptive statistics. Listings will also be provided for individual subjects.

Unit Conversion:

Weight (Kg) = 0.4536\* Weight (lb)

Height (Cm) = 2.54\* Height (In)

### **17.5 Physical Examination**

Listing will be provided for the Physical examination.

### **17.6 Neurological Examination**

Neurological examination parameters for systems affected

- Pyramidal function (Yes / No)
- Cerebellar function (Yes / No)
- Brain stem function (Yes / No)
- Sensory function (Yes / No)
- Bowel and bladder function (Yes / No)
- Visual (optic) function (Yes / No)
- Cerebral (mental) function (Yes / No)

will be summarized as number and percentage at all available visits from Safety Analysis Set. Listings will also be provided for the individual subjects.

**18. Benefit risk assessment**

Not applicable

**20. Appendices**

- TSQM Version II Analysis
- MusiQoL scoring algorithm
